13.7.3 Unblinded Interim Efficacy Analysis (Adaptive Design)

After 50% of Subjects are treated and followed for 6 months, an interim unblinded analysis comparing treatments on the 6-month short term outcome will be carried out. There will be no provision to stop the study at interim stage for overwhelming effectiveness and hence no adjustment of the significance level for the final analysis. The first purpose of the interim analysis is to calculate the power for non-inferiority, conditioned on the interim short term outcome rates in each treatment and on the non-inferiority margin of 10%. If conditional power is <50% or >80%, the study will continue as is; if conditional power is between 50-80%, the sample size will be re-estimated to maintain conditional power of 80% for the 6-month short term endpoint, controlling Type I error following the method in Wang et al¹⁰. Any sample size increase will then be applied to the long term endpoint.

13.8 Subgroup Analysis

Once the analyses comparing the treatment arms are complete, a series of subgroup analyses will be performed, assessing treatment difference within each subgroup. Each subgroup will be evaluated for the primary composite endpoint, survival, adverse events, device malfunction, quality of life and functional status, as described above. Subgroups will include but may not be limited to:

- Gender: Males vs Females
- Race: Caucasian/White vs African-American/ Black vs Other
- Age: 18 – 59 vs 60 – 75 vs > 75 years
- Intended Use at implant as defined by Appendix 6
- VO2 max
- INTERMACS Profile

The purpose of the subgroup analyses is not to reach a statistically significant result within each subgroup, but rather to assess consistency of treatment difference across subgroups.

13.9 Analysis of Survival and Subject Outcome

Overall survival will be assessed for each of the two treatments using the Kaplan-Meier product-limit method. Differences between treatments in survival distributions will be analyzed using a logrank test. Subjects surviving will be censored at last known follow-up time point.

A competing outcome graph will be prepared at 6 months for short term results and 24 months for long term results.

13.10 Analysis of Adverse Events

All pre-defined adverse events will be captured. Tables will be created for HM3 and HM II AEs that show the by-treatment incidences of all adverse events and the by-treatment event rate per patient year of support. Serious adverse events (SAEs) will be analyzed in a similar manner as AEs. Differences in event rates between the treatment arms will be analyzed using Fisher's Exact test or Poisson regression, as appropriate.

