
Study Follow-up Intervals
	
Screening, Baseline, Implant, Post-op Day 1, 1 week, Discharge, Month(s) 1, 3, 6, 12, 18 and 24.

STUDY SYNOPSIS	
Data Collection	A 21 CFR part 11 compliant Electronic Data Capture (EDC) system will be used to collect data.
Statistical Analysis	
Baseline data will be analyzed using Fisher's exact test and unpaired t-tests as appropriate. The HM3 will be considered non-inferior to the HM II for short term and long term indications if the lower 95% confidence limit of the difference between the success for the HM3 and HM II is greater than the non-inferiority margin of -10%. Once non-inferiority is inferred, the data will be analyzed for superiority using closed testing methods.
 
Differences in survival between treatment groups will be analyzed using the Kaplan-Meier product-limit method.
 
Safety, including device malfunctions, will be reported as incidence and event rate per patient year of support. A time to event analysis will also be performed. Comparison of adjudicated adverse events between HM3 and the HM II control group will be performed using Fisher's exact test or Poisson regression, as appropriate.
 
Quality of Life and six minute walk data will be analyzed using mixed models.
 
Subanalyses of the primary endpoints, survival, adverse events, and quality of life will also be performed and will include gender, ethnicity, age, VO2 Max, and intended use of the device at the time of implant as defined by INTERMACS.
 
In addition to the primary outcome, the study will be powered to test if HM3 pump reliability is superior to HM II by analyzing the incidence of pump replacement. The percentage of HM3 pump replacements will be compared to HM II using Fisher's exact test.

Adverse Events	Anticipated adverse events will be captured using definitions described in this FDA approved protocol.
Adaptive Design	In case the assumptions of the study are incorrect, a pre-specified early look at the data will be performed by an independent statistician to determine if the study requires adjustment to the sample size. The adaptive design analysis will be performed to evaluate the conditional power.
Number of Investigational Sites	Up to 70 U.S. sites

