10.2 Secondary Study Endpoints

- Quality of Life: Quality of Life as measured by the EuroQoL-5D-5L (EQ-5D-5L) and the Kansas City Cardiomyopathy Questionnaire (KCCQ)
- Functional Status: Functional status as measured by the Six Minute Walk Test (6MWT) and by NYHA Classification.
- Adverse Events: Frequency, incidence and rates of pre-defined anticipated adverse events
- Device Malfunctions: Frequency and incidence of device malfunctions
- Reoperations: Frequency and incidence of all reoperations
- Rehospitalizations: Frequency and incidence of all rehospitalizations

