APPENDIX 1: ANTICIPATED ADVERSE EVENT DEFINITIONS

Bleeding

An episode of SUSPECTED INTERNAL OR EXTERNAL BLEEDING that results in one or more of the following:

- a. Death,
- b. Reoperation,
- c. Hospitalization,
- d. Transfusion of red blood cells as follows:
 - If transfusion is selected, then apply the following rules:

During first 7 days Post-implant

- ≥ 50 kg: ≥ 4U packed red blood cells (PRBC) within any 24 hour period during first 7 days post-implant.
- <50 kg: ≥20 cc/kg packed red blood cells (PRBC) within any 24 hour period during the first 7 days post-implant

After 7 days Post-implant*

- Any transfusion of packed red blood cells (PRBC) after 7 days following implant with the investigator recording the number of units given. (Record number of units given per 24 hour period).

Note: Hemorrhagic stroke is considered a neurological event and not as a separate bleeding event.

*Any transfusion of ≥ 2U packed red blood cells (PRBC) after 7 days following implant will be considered a serious bleed

Cardiac Arrhythmias

Any documented arrhythmia that results in clinical compromise (e.g., diminished VAD flow, oliguria, pre-syncope or syncope) that requires hospitalization or occurs during a hospital stay. Cardiac arrhythmias are classified as 1 of 2 types:

- 1) Sustained ventricular arrhythmia requiring defibrillation or cardioversion.
- 2) Sustained supraventricular arrhythmia requiring drug treatment or cardioversion.

Pericardial Fluid Collection

Accumulation of fluid or clot in the pericardial space that requires surgical intervention or percutaneous catheter drainage. This event will be subdivided into those with clinical signs of tamponade (e.g. increased central venous pressure and decreased cardiac/VAD output) and those without signs of tamponade.

Device Malfunctions

A Device Malfunction occurs when any component of the MCS system ceased to operate to its designated performance specifications or otherwise fails to perform as intended. Performance specifications include all claims made in the Instructions for Use.

Internal Component Malfunction: Malfunction of any device system component that is implanted within the patient. A malfunction to these components may require further surgery to repair or replace.

External Component Malfunction: Malfunction of a device system component that is used external to the patient and can be replaced or repaired without the need for further surgery.

Device Thrombosis

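### The Poisson comparison of adverse-event rates names no variance that allows for repeat events in one patient, so intervals for frequent events such as bleeding could be too narrow

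*Protocol*

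**What the plan says.** Protocol 13.10 and SAP 8.9 tabulate two measures by arm: incidence and "the by-treatment event rate per patient year of support". Both then compare the arms by Fisher's "Exact test or Poisson regression, as appropriate". The synopsis has the same pair of measures, saying that safety "will be reported as incidence and event rate per patient year of support". It also has the same pair of tests: "Comparison of adjudicated adverse events between HM3 and the HM II control group will be performed using" Fisher's "exact test or Poisson regression, as appropriate". The synopsis adds: "A time to event analysis will also be performed".

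Protocol Appendix 1 defines bleeding as "An episode of SUSPECTED INTERNAL OR EXTERNAL BLEEDING that results in one or more of the following" (death, reoperation, hospitalization or transfusion). The unit is an episode, so one patient can contribute several.

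Protocol 10.2 lists as a secondary endpoint "Frequency, incidence and rates of pre-defined anticipated adverse events". The corresponding SAP list (5.3) names frequency and incidence but not rates, although SAP 8 and 8.9 still report rates. Protocol 13.14 and SAP 8.13 test each secondary endpoint at two-sided 0.05 without multiplicity adjustment.

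Neither document mentions over-dispersion, a scale parameter, a robust or clustered variance, a negative binomial model or any other recurrent-event method.

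**The concern.** Fisher's test compares the share of patients with an event. It cannot compare events per patient-year, so Poisson regression is the only method named for rates. With its ordinary variance, that model treats a patient who has already bled as no more likely than anyone else to bleed again. If some patients are more prone to events than others, the counts vary more than the model allows. The standard error of the log rate ratio is then too small, the confidence interval too narrow and the p-value too low.

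The error has no preferred direction. It could make the new pump look safer or less safe than the data support. The same method applies to serious adverse events and carries into the subgroup analyses.

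**Working it through.** The plan states no power, sample size or interval width for this comparison, so there is no figure of its own to reproduce.

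**Inputs from the documents.** Protocol Table 1 gives 24-month incidences of 62% for bleeding and 7% for device thrombosis. These are upper 99% bounds from post-approval studies of the control device. The test level is two-sided 0.05. There are 183 patients per arm in the long-term cohort and 514 in the full cohort.

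**Assumed input.** Let *v* be the between-patient (frailty) variance of the event rate, relative to a mean of 1. The documents do not give it, so 0.1, 0.25, 0.5 and 1.0 are shown. A value of zero means no clustering and no error.

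**Formula.** Take gamma-distributed patient rates and complete 24-month follow-up, with mean count *m*.

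- P(no event) = (1 + *vm*)^(−1/*v*) = 1 − *p*, so 1 + *vm* = (1 − *p*)^(−*v*).
- The variance of the count is *m*(1 + *vm*), against *m* under Poisson.
- Ratio of correct to Poisson standard error = √(1 + *vm*) = (1 − *p*)^(−*v*/2).
- False-positive rate = 2 × [1 − Φ(1.96 / ratio)].

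Only the total count enters, so the timing of events within the 24 months does not matter.

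**Results for bleeding, *p* = 0.62**

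| *v* | SE ratio = 0.38^(−*v*/2) | 1.96 / ratio | False-positive rate |
|---|---|---|---|
| 0.1 | 1.05 | 1.87 | 6.2% |
| 0.25 | 1.13 | 1.74 | 8.2% |
| 0.5 | 1.27 | 1.54 | 12.4% |
| 1.0 | 1.62 | 1.21 | 22.7% |

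Because 62% is an upper bound, the same calculation at *p* = 0.50 gives 5.8%, 7.2%, 9.9% and 16.6%.

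**Device thrombosis, *p* = 0.07.** At *v* = 1.0 the ratio is 0.93^(−0.5) = 1.04 and the false-positive rate 5.9%. Smaller *v* gives less.

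**Simulation check.** This used 6,000 trials per setting, equal true rates, a constant event rate set so that risk over a full 24 months is 62%, and about 47% of patients leaving before 24 months.

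| Patients per arm | *v* | Ordinary variance | Robust variance |
|---|---|---|---|
| 183 | 0.5 | 11.7% | 5.1% |
| 183 | 1.0 | 20.7% | 4.9% |
| 514 | 0.5 | 11.5% | 5.1% |
| 514 | 1.0 | 21.4% | 5.6% |

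The simulation agrees with the closed form. A larger sample does not remove the problem, and a robust variance does.

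**Sparse events.** A rate model cannot be required for every event type. At an assumed 1% incidence and 183 per arm, about 1.83 events are expected in each arm. The chance that at least one arm has none is 1 − (1 − e^(−1.83))² ≈ 30%. The log rate ratio and its robust interval then do not exist.

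**The case against.** **The text is silent on the variance; it does not state a wrong one.** This stands. Poisson regression with a robust variance is still Poisson regression and is compatible with the wording. A reader might infer that the plan prescribes the naive variance, but the documents do not say so. The model-based variance is only the ordinary reading. What is missing is a stated choice, and in an unblinded trial that choice is better made before results are seen.

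**The consequence is limited.** This also stands. Protocol sections 1 and 25 describe reduced adverse events as a descriptive evaluation. SAP section 7 rules out statistical claims on secondary endpoints. Many event types are compared without multiplicity adjustment, and rates are missing from the SAP's endpoint list. Against this, intervals and p-values will still be produced, and they should be valid for what they report.

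**The size rests on an assumed dispersion.** True, and small inflation fits the documents as well as large. A reader might also infer error rates of up to a third for bleeding. Such figures (about 33% at *v* = 1.0) need only 35% of patients still on support at 24 months, 62% read as the incidence observed during that shortened support, and a constant event rate. Table 1, with bleeding at 56% by 6 months and 62% by 24, does not support a constant rate, although its two columns come from different cohorts. The complete-follow-up figures avoid that assumption and are the ones to rely on.

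**Conclusion.** The point holds as a minor one. The plan names Poisson regression for rates of events that can recur in a patient, and it states no variance that allows for this. If the ordinary variance is used, nominal 5% tests for bleeding would run at about 6% to 23% over the assumed frailty variances of 0.1 to 1.0, given 62% incidence and complete follow-up. At 50% incidence the range is about 6% to 17%. Rare events are hardly affected.

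The conclusion depends on two things that the documents do not settle: which variance the analyst would use, and how far patients differ in their tendency to have events.

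A reader might infer that the trial's main conclusions are at risk. They are not. The primary non-inferiority tests, the powered pump-replacement test, the sample sizes and the planned time-to-event safety analysis (if it is time to first event) do not use this method.

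**What to change.** In Protocol 13.10 and SAP 8.9, replace the final sentence with:

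> The proportion of Subjects with at least one event will be compared between arms by Fisher's exact test. Where event rates per patient-year of support are compared by Poisson regression, the model will use log time on support as offset and a subject-level robust (sandwich) variance. Where events are too sparse for the model (for example, no events in one arm), only Fisher's exact test on the proportion of Subjects will be used.

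Make the same change in the synopsis, keeping its restriction to adjudicated events.

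The cost is a short text change in three places and one model option, with no new data. The downside is wider intervals where events cluster: for bleeding with complete follow-up, by the standard-error ratios tabulated above. Where there is no clustering, the simulated robust-to-Poisson standard-error ratio was 0.98 to 1.00 for the events tested (7% to 62% incidence), so essentially nothing is lost. Rarer events were not tested, and the sparse-event sentence covers them.

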13.11 Analysis of Device Malfunctions

All suspected HM3 device malfunctions will be reported. Thoratec will ask that all explanted devices be returned for analysis. Data on device malfunctions will be analyzed and tables will be created that report the following:

- Events that are confirmed by analysis of the device by Thoratec engineers
- The component of the device involved
- Days to the malfunction
- Action taken in response to the malfunction
- Reoperations due to malfunction
- Death due to malfunction

13.12 Analysis of Pre-Implant Data

Tables will be created to define the study population at baseline. Tables will include demographics, all laboratory assessments, all hemodynamic assessment, cardiac history, INTERMACS profile, and concurrent interventions (Cardiac Resynchronization Therapy (CRT), Automatic Internal Cardiac Defibrillator (AICD), IABP, Inotropes, etc). The intended use of the device at implant will also be collected, as defined by INTERMACS (Appendix 6). Baseline data will be compared between treatment groups using unpaired t-tests or Fisher's exact test as appropriate.

13.13 Analysis of Implant and Discharge Data

Time on cardiopulmonary bypass during implant surgery will be collected and reported as a median, quartiles and range. All concurrent procedures carried out during implant surgery will be reported. Length of Stay (LOS) will be defined as the time from implant to discharge. LOS will be reported as a mean with standard deviation, median, quartiles and range. The time on cardiopulmonary bypass and LOS will be compared between treatment groups using the Wilcoxon Rank Sum test.

13.14 Analysis of Secondary Endpoints

Secondary endpoints will each be tested at the two-sided 0.05 level of significance. There will be no adjustment for multiple comparisons across the secondary endpoints. There will be no imputation of missing data for the secondary endpoints.

13.14.1 Pump Hemodynamics

The mean flow and pump index (flow/BSA) with standard deviation for the HM3 and HM II Subjects will be plotted over time. At each time point, treatments will be compared using the unpaired t-test.

13.14.2 Laboratory values

Mean laboratory values with standard deviations for HM3 and HM II Subjects will be plotted over time. At each time point, treatments will be compared using the unpaired t-test.

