16 STUDY PROCEDURES AND ASSESSMENTS

Participating centers will utilize their own local laboratories for protocol required laboratory assessments, and will be instructed to follow their institution's requirements for maintenance and/or calibration of laboratory equipment.

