16.2 Baseline Assessments

The following baseline assessments will be performed within 30 days prior to implant (refer to Section 34, Table 2 for the Study Visit Schedule):

1. Medical History, including cardiovascular history with etiology of HF and duration of HF
2. Physical Exam, including height, weight and vital signs
3. Current Medications (total daily dose): anticoagulation/anti platelet, antibiotics, and cardiovascular medications including ACE inhibitors, ARBs, beta blockers, statins, nitrates, allopurinol, aldosterone blockers, and diuretics including metolazone, hydrochlorothiazide and furosemide
4. Laboratory Assessments:
 - a. Hematology: hemoglobin, hematocrit, percent lymphocytes, platelet count, WBC, PHgb, Bleeding/Coagulation: INR, aPTT/PTT, PT
 - b. Chemistry: Potassium, Blood Urea Nitrogen (BUN), creatinine, uric acid, sodium, eGFR (calculated), serum BNP or NT-proBNP, total protein, albumin or pre-albumin, CRP or hs-CRP
 - c. Lipids: cholesterol
 - d. Liver Enzymes: LDH, AST, ALT, total bilirubin
5. Hemodynamic Measurements
6. Echocardiogram: LVEF, LVEDD, LVESD, AV opening, AI, MR, TR including severity and/or grade.
7. Electrocardiogram (ECG): Heart Rate, QRS duration, Arrhythmias
8. 6 Minute Walk Test (6MWT) (if Subject is able; reason must be provided if not performed)

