29.7 Laboratory Accreditation and Normal Values

Before initiation of the study, appropriate accreditation for all laboratories to be used in the study will be requested by Thoratec. Throughout the study, the Investigator shall provide Thoratec documentation of all renewals of accreditation. The range of values considered normal for the laboratory tests being performed for the study must be provided to Thoratec in order to allow the data to be pooled.

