 - xi. Intolerance to anticoagulant or antiplatelet therapies or any other peri/post-operative therapy the investigator will require based upon the patients' health status

- xii. Presence of any one of the following risk factors for indications of severe end organ dysfunction or failure:
 - 1. An INR \geq 2.0 not due to anticoagulation therapy
 - 2. Total bilirubin $>$ 43 $\mu\text{mol/L}$ (2.5 mg/dl), shock liver, or biopsy proven liver cirrhosis
 - 3. History of severe chronic obstructive pulmonary disease (COPD) defined by $\text{FEV}_1/\text{FVC} < 0.7$, or $\text{FEV}_1 < 50\%$ predicted
 - 4. Fixed pulmonary hypertension with a most recent PVR \geq 8 Wood units that is unresponsive to pharmacologic intervention
 - 5. History of stroke within 90 days prior to enrollment, or a history of cerebrovascular disease with significant ($> 80\%$) carotid artery stenosis
 - 6. Serum creatinine \geq 221 $\mu\text{mol/L}$ (2.5 mg/dl) or the need for chronic renal replacement therapy
 - 7. Significant peripheral vascular disease (PVD) accompanied by rest pain or extremity ulceration
- xiii. Patient has moderate to severe aortic insufficiency without plans for correction during pump implant
- xiv. Pre albumin $<$ 150 mg/L, or Albumin $<$ 30g/L (3 g/dL)
- xv. Planned Bi-VAD support prior to enrollment
- xvi. Patient has known hypo or hyper coagulable states such as disseminated intravascular coagulation and heparin induced thrombocytopenia
- xvii. Participation in any other clinical investigation that is likely to confound study results or affect the study
- xviii. Any condition other than HF that could limit survival to less than 24 months

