8.13.2 Laboratory values

Mean laboratory values with standard deviations for HM III and HM II Subjects will be plotted over time. At each time point, treatments will be compared using the unpaired t-test.

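### Laboratory values are compared by visit-wise t-test on raw means without the baseline value already collected, which loses precision (minor)

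*Protocol*

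**What the plan says.** The two documents give the same rule. Protocol 13.14.2: "Mean laboratory values with standard deviations for HM3 and HM II Subjects will be plotted over time". SAP 8.13.2: "Mean laboratory values with standard deviations for HM III and HM II Subjects will be plotted over time", followed by "At each time point, treatments will be compared using the unpaired t-test". Neither names a transformation, a baseline covariate or a longitudinal model. The parent sections (Protocol 13.14, SAP 8.13) set a two-sided 0.05 level, with no multiplicity adjustment and no imputation.

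The laboratory panel is taken at baseline (Protocol 16.2) and at eight scheduled visits after implant, from 1 week to 720 days (Protocol 34, Table 2). The chemistry list lets a site choose within three pairs: "serum BNP or NT-proBNP, total protein, albumin or pre-albumin, CRP or hs-CRP". On where the tests are run, Protocol 16 says: "Participating centers will utilize their own local laboratories for protocol required laboratory assessments". Under Protocol 29.7 the local normal ranges "must be provided to Thoratec in order to allow the data to be pooled".

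Other outcomes are handled differently. Six-minute walk, EQ-5D-5L and KCCQ use mixed models that refer each assessment to baseline (Protocol 13.15.2, 13.16; SAP 8.14.2, 8.15). For two other continuous measures, Protocol 13.13 uses a rank test: "The time on cardiopulmonary bypass and LOS will be compared between treatment groups using the Wilcoxon Rank Sum test".

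**The concern.** Two features of the laboratory rule give away precision that the trial has already paid for.

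- **Baseline is left out of the follow-up comparison.** A baseline value that correlates with the follow-up value explains part of its variance, and a t-test on follow-up values alone leaves that part in the error term.
- **The scale is raw.** BNP, NT-proBNP, LDH, plasma free hemoglobin and CRP can be expected to have a long right tail. The documents give some support for LDH and plasma free hemoglobin. The hemolysis definition in Appendix 1 needs plasma free hemoglobin above 40 mg/dl with LDH above three times the upper limit of normal. Table 1 expects hemolysis in up to 11% and device thrombosis in up to 7% by 24 months. A small group with extreme values can then dominate a mean and its SD.

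There is also a gap in wording. Sites may choose within a pair of analytes, and no sentence says that the two are analysed separately.

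What is at stake is the sensitivity and readability of descriptive laboratory comparisons. LDH and plasma free hemoglobin have some interest because Protocol 13.5.1 expects less thrombus with the new pump. No primary or powered analysis depends on them.

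**Working it through.** The documents give no SD, effect size, correlation or power for laboratory values, so there is no planned figure to reproduce. Every size below rests on a stated assumption.

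**1. Baseline adjustment.** With correlation ρ between baseline and follow-up, adjustment multiplies the residual variance by 1 − ρ². The difference detectable with 80% power at two-sided 0.05 is (1.96 + 0.84) × √(2(1 − ρ²)/n), in SD units. Take n = 183 per arm, the long-term cohort in SAP 8.4.3:

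| ρ (assumed) | Variance removed | Detectable difference | Power at 0.293 SD |
|---|---|---|---|
| not adjusted | 0 | 2.80 × √(2/183) = 0.293 SD | 80% |
| 0.3 | 9% | 0.279 SD | 84% |
| 0.5 | 25% | 0.254 SD | 90% |

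**2. Log scale.** Simulation of a log-normal marker with 4,000 trials per setting, two-sided 0.05 and 120 per arm. The 120 is an assumed number with a value at one visit; it is not a figure from the plan.

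| True ratio | Log-SD (assumed) | Raw t-test | t-test on logs | Gap, points |
|---|---|---|---|---|
| 1.4 | 0.8 | 80% | 91% | 11 |
| 1.4 | 1.0 | 53% | 75% | 22 |
| 1.4 | 1.2 | 35% | 59% | 24 |
| 1.3 | 1.0 | 36% | 52% | 16 |

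A repeat with another seed gave gaps of 11, 18 and 23 points in the three rows at ratio 1.4. At log-SD 0.5 and ratio 1.4 both tests are at essentially 100%, so there is no gap. At 183 per arm, ratio 1.4 and log-SD 1.0, power is 71% against 89%. With no true difference, the raw t-test rejected in 4.5-5.0% of trials at 120 per arm, so the planned test is valid.

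**3. Both together.** 183 per arm, true ratio 0.75, ρ = 0.5, one assay, 2,000 trials:

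| Log-SD (assumed) | Raw t-test | t-test on logs | Logs with baseline |
|---|---|---|---|
| 0.8 | 84% | 94% | 98% |
| 1.0 | 59% | 81% | 90% |

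**4. The paired analytes.** The exclusion cut-offs are pre-albumin 150 mg/L and albumin 30 g/L. In one unit, 30 g/L = 30,000 mg/L, and 30,000/150 = 200. The two cannot share a mean. As a what-if, suppose half the subjects in each arm were on a scale 3, 6 or 10 times larger and the values were pooled. In the setting of step 3 at log-SD 1.0, raw t-test power would fall from 59% to 45%, 33% or 31%. Across both log-SDs, the rejection rate with no true difference was 1.6-4.1%. Even then the harm would be lost power and an uninterpretable mean.

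**The case against.** The strongest reply is that little depends on these comparisons. Laboratory values are in neither list of secondary endpoints (Protocol 10.2, SAP 5.3), have no hypothesis or sample size, and SAP 7 rules out statistical claims from secondary endpoints. The thrombus rationale is examined more directly by the powered pump-replacement analysis and by hemolysis and device thrombosis as defined events. That stands, and it sets the severity.

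It is also fair to say that the sizes are assumed and that log-normal data favour a log-scale test by construction. That stands too. The direction of the baseline gain does not depend on log-normality, but its size depends on a correlation the documents do not give.

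A reader might infer more than the text supports:

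- **That BNP and NT-proBNP, or albumin and pre-albumin, will be averaged together.** The either/or wording governs collection, and the exclusion criteria give albumin and pre-albumin separate limits. The analysis text is silent, so this is a missing sentence and not a stated plan. CRP and hs-CRP are a weak example: the abbreviation list shows one protein at two assay sensitivities.
- **That the comparison is biased.** Randomization is stratified by center and laboratories are local, so assay differences between centers should balance across arms. The simulations show no inflation of type I error.
- **That baseline laboratory values are ignored.** They are tabulated and compared between arms (Protocol 13.12, SAP 8.11). They are absent only from the follow-up comparison.
- **That medians are not reported.** The general rules in Protocol 13.1 and SAP 8 already give median, minimum and maximum for continuous data.
- **That a subject who changes assay invalidates a change score.** No within-subject laboratory change is planned.

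**Conclusion.** The concern holds as a minor, nearly free improvement. The visit-wise t-test on raw means is valid but inefficient, and it differs from how the plan treats its other repeated continuous outcomes. Baseline adjustment would remove about 9-25% of residual variance if the correlation is 0.3-0.5. For skewed markers, the raw scale costs about 11-24 points of power at log-SD 0.8-1.2, ratio 1.4 and 120 per arm, and nothing at log-SD 0.5 or less. These inputs are assumptions. There is no evidence of bias or of an inflated false-positive rate, and no conclusion about the primary endpoints or the powered secondary endpoint is affected.

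**What to change.** In Protocol 13.14.2 and SAP 8.13.2:

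1. Replace the t-test at each visit with a baseline-adjusted comparison: ANCOVA at each visit, or one mixed model with baseline as a covariate.
2. Use the log scale for BNP, NT-proBNP, LDH, plasma free hemoglobin and CRP, and report geometric mean ratios with 95% confidence intervals. LDH may be expressed as a multiple of the local upper limit, using the ranges collected under Protocol 29.7.
3. State that BNP and NT-proBNP, and albumin and pre-albumin, are analysed as separate analytes, each in common units.
4. State how subjects without a baseline value of the analyte are handled. The rule must fit the ban on imputation in Protocol 13.14 and SAP 8.13. A mixed model that treats baseline as one of the responses would keep these subjects without imputing.

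The cost is SAP wording and a little programming, with no new samples and no change to site procedures. For the logged markers, results become ratios instead of differences in means.
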